Subjects who have previously completed The RESTFUL Study are consented to one of three Arms, the design of which is illustrated in the flowchart below (Figure 1). Arm 1 is a Direct Roll-Over Extension, Arm 2 is a Control, and Arm 3 is a Delayed Extension. A subject may be asked to participate in Arm 3 after completing Arm 2.

Investigational Plan, Protocol CT-05 (Extension Study)

Document #: CT-4

Rev: 1.0

Effective: 11/24/2021

Arm 1 (Direct Roll-Over Extension) – Arm 1 is only an option for subjects who successfully
complete The RESTFUL Study after enrollment to CT-05 begins at a given clinical site; Arm 1
involves a 24-wk extension period of NTX100 device use followed by an 8-wk period without
device use.

- Arm 2 (Control Group) Arm 2 is an option for subjects who successfully complete the RESTFUL Study before enrollment to CT-05 begins at a given clinical site or subjects who decline to participate in Arm 1. Subjects enrolled in Arm 2 will not receive treatment with the NTX100 device. Arm 2 involves follow-up phone calls to access on RLS progression and medication usage at 8-wks, 16-wks, and 24-wks after the end of The RESTFUL Study. Subjects who are consented more than 8-wks after The RESTFUL Study completion will only complete the remaining follow-ups (e.g. subjects consented 12-wks after The RESTFUL Study will only complete the 16-wk and 24-wk follow-ups).
- Arm 3 (Delayed Extension) Arm 3 is only an option for subjects who successfully complete The RESTFUL Study before enrollment to CT-05 begins at a given clinical site; like Arm 1, Arm 3 involves a 24-wk extension period of NTX100 device use followed by an 8-wk period without device use. Enrollment in Arm 3 of the study begins after a fixed delay upon close-out of the RESTFUL Study; the fixed delay will be >= 24-wks and <= 52-wks, will be the same value for all subjects (+/- 2-wks), and will be determined based on investigational device availability and other constraints. The sponsor will notify each site once Arm 3 is open to enroll study subjects for that site.

•

[figure not shown]
Investigational Plan, Protocol CT-05 (Extension Study)

Document #: CT-4

Rev: 1.0

Effective: 11/24/2021

Figure 1: Study Design Flowchart

5. Blinding

Arms 1 and 3 will be open label. The treatment assignment on each device will be set to Active for all subjects and subjects will be informed that they are received Active treatment.

Arm 2 does not involve treatment.

6. Duration

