16.2. Comparison of Study Arms

Arms 1 and 3 involve identical procedures, with the following exceptions:

- Eligibility
 - a. [Arm 1] Only open to subjects who complete the RESTFUL Study after this protocol opens to enrollment at a given site and thus can directly enter this protocol.

Clinical Trial

Investigational Plan, Protocol CT-05 (Extension Study)

Document #: CT-4

Rev: 1.0

Effective: 11/24/2021

b. [Arm 3] Only open to subjects who completed the RESTFUL Study before this protocol opens to enrollment at a given site - and thus have some delay before entering this protocol). Subjects who have completed Arm 2 remain eligible for Arm 3.

Delay

- a. [Arm 1] There is typically no delay between RESTFUL Study completion and Arm 1 entry. A delay of up to 2-days is permitted if needed.
- b. [Arm 3] There is a fixed delay between RESTFUL Study completion and Arm 3 entry. The fixed delay will be >= 24-wks and <= 52-wks, will be the same value for all subjects (+/- 2-wks), and will be determined based on investigational device availability and other constraints.

Baseline

- a. [Arm 1] Baseline refers to RESTFUL Study entry (Eval 1 of RESTFUL Study).
- b. [Arm 3] Baseline refers to entry to this protocol (Eval 1 of this protocol).

Assessments at Eval 1

- a. [Arm 1] The IRLS and MOS-Sleep data from are not administered at Eval 1, because they are administered on the same day at Restful Study Eval 11.
- b. [Arm 3] The IRLS and MOS-Sleep are administered at Eval 1.

Arm 2 differs significantly from Arm 1 and 3:

Eligibility

- a. [Cohort 2A] Subjects who completed the RESTFUL Study after this protocol opens to enrollment are eligible for Arm 2 only if they decide not to participate in Arm 1. All subjects in this group are first given the choice to participate in Arm 1 without knowledge of the alternative Arm 2.
- b. [Cohort 2B] All subjects who completed RESTFUL Study less than 24-wks before this protocol opens to enrollment are eligible for Arm 2.

Delay

Investigational Plan, Protocol CT-05 (Extension Study)

Document #: CT-4

Rev: 1.0

Effective: 11/24/2021

- a. [Cohort 2A] There is typically no delay between RESTFUL Study completion and Arm 2 entry. A delay of up to 2-days is permitted if needed.

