- b. [Cohort 2B] There is a variable delay between RESTFUL Study completion and Arm 2 entry, depending on the time that the subject completed the Restful Study. Subjects will be enrolled either 8-wks, 16-wks, or 24-wks after completion of the RESTFUL Study, +/- 1-wk.

Completion

a. Both Cohorts 2A and 2B are completed 24-wks after completion of the RESTFUL Study
 +/- 1-week. Therefore, the duration of study participation in Arm 2 depends on the delay between RESTFUL Study completion and enrollment in this study.

Baseline

a. For both Cohorts 2A and 2B, baseline refers to RESTFUL Study entry (Eval 1 of Restful Study).

Table 3. Comparison of Study Arms

	Arm 1	Arm 2	Arm 3 Earlier cohort of RESTFUL Study subjects		
Eligibility	Later cohort of RESTFUL Study subjects	RESTFUL Study subjects who don't complete Arm 1			
Start date relative to RESTFUL Study completion	0* days	Less than 24-wks	Fixed delay, >=24-wks and <=52-wks		
End date relative to RESTFUL Study completion	32-wks	24-wks	Variable		
Duration	32-wks	up to 24-wks	32-wks		
Investigational device use	Wks 1-24	None	Wks 1-24		
Baseline	RESTFUL Study entry	RESTFUL Study entry	Entry to this study		

^{*} Up to 2 days if needed

Investigational Plan, Protocol CT-05 (Extension Study)

Document #: CT-4

Rev: 1.0

Effective: 11/24/2021

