Evaluation 1: In-person visit or Phone call for enrollment, including consent, screening, and assessments. For Cohort 2A (see Section 16.2), consent & screening will typically occur in-person on the same visit as Eval 11 for the RESTFUL Study. If the subject's schedule does not permit completion of assessments during this office visit, then these assessments may be conducted via phone follow-up at any time within the 3-days following the office visit.

Evaluation 2: (8-wks after completion of the RESTFUL Study) Phone follow-up to assess RLS symptoms, any changes to daily medications, and adverse events.

Evaluation 3: (16-wks after completion of the RESTFUL Study) Phone follow-up to assess RLS symptoms, any changes to daily medications, and adverse events.

Evaluation 4: (24-wks after Eval #1) Phone follow-up to assess RLS symptoms, any changes to daily medications, and adverse events. Study exit.

Investigational Plan, Protocol CT-05 (Extension Study)

Document #: CT-4

Rev: 1.0

Effective: 11/24/2021

As summarized in Table 5, enrollment to Arm 2 will either occur at either 0-wks (EVAL 1), 8-wks (EVAL 2), 16-wks (EVAL 3), or 24-wks (EVAL 4) after completion of the Restful Study, +/- 6-days. If enrollment occurs at 24-wks, the SF-36 and concomitant medication assessments will only be conducted once.

Table 5. Structure of Arm 2

Delay after RESTFUL study completion	Evals conducted
0-wks	1,2,3,4
8-wks	1,2,3,4
16-wks	1,3,4
24-wks	1,4

TABLE 2: SCHEDULE OF ASSESSMENTS FOR ARM 2

Schedule of assessment	s - Arm 2						
		Eval 1	Eval 2	Eval 3	Eval 4		
		Day 0	Wk-8*	Wk-16*	Wk-24*		
		In-person or					
Assessment	Completed by	Remote	Remote	Remote	Remote		
Screening		Х					
Consent		Х					
Study entry question naire	Staff + subject	X					
ConMeds	Staff	X	х	Х	Х		
AE Monitoring/Reporting	Staff		х	х	х		
IRLS	Staff + subject		х	х	х		
PGFI	Staff + subject		Х	Х	Х		
CGFI	Investigator		х	Х	Х		
MOS-Sleep	Staff + subject		Х	Х	Х		
SF-36	Staff + subject	X			Х		
Study exit questionnaire	Staff + subject				х		
* Duration after Eval 11 of The	RESTF UL Study, not CT-4 enrollm	ent [not all subjects will en	roll in time	to complet	e Wk-8 or \	Wk-16 timepoints	

16.13. Device replacement in Arms 1 and 3

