6.2 Stable Medication Population

The Stable Medication (SM) Population will include all eligible subjects who pass screening, are enrolled into the study, and do not report any of the following changes to prescription RLS medication between completion of the RESTFUL Study and Week 24 of CT-05:

- 1. New prescription RLS medication.
- 2. Change in dose of prescription RLS medication.
- 3. New prescription sleep medication.
- 4. Change in dose of prescription sleep medication.

The Stable Medication Population will be used for a secondary analysis of key secondary efficacy endpoints #6-11. This is intended to account for the differences in instructions regarding changes to prescription medications for Arms 1 and 2.

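### The Arm 2 entry window contradicts itself, and admits controls at 24 weeks, when consent, the Week 24 outcome and study exit coincide; key secondary endpoints #6-11 take no account of this

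*Protocol*

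**What the plan says.** Four places in the protocol set the time of entry to Arm 2.

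- Table 3 gives the start date relative to RESTFUL completion as "Less than 24-wks".
- Section 16.2, for Cohort 2B: "Subjects will be enrolled either 8-wks, 16-wks, or 24-wks after completion of the RESTFUL Study, +/- 1-wk".
- Section 16.12 allows entry at 0, 8, "16-wks (EVAL 3), or 24-wks (EVAL 4) after completion of the Restful Study, +/- 6-days".
- Table 5 assigns Evals 1 and 4 only to a subject who enters at 24 weeks, and the text above it says: "If enrollment occurs at 24-wks, the SF-36 and concomitant medication assessments will only be conducted once".

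Section 16.2 also fixes the end of the arm: "Both Cohorts 2A and 2B are completed 24-wks after completion of the RESTFUL Study". Section 16.10 states that medication data are reported by the subject.

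Protocol 17.2.4 lists the comparison of Arm 1 with Arm 2 under additional analyses. SAP 4.2 makes it key secondary endpoints #6-11, and SAP 8.2 tests these at one-sided 0.025. SAP 5.2 rules out covariate adjustment. SAP 6.2 builds the Stable Medication population, used for a secondary analysis of #6-11, from changes reported "between completion of the RESTFUL Study and Week 24 of CT-05". The SAP does not mention that Arm 2 subjects enter at different times.

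**The concern.** The two arms are sampled differently in time. An Arm 1 subject consents about 24 weeks before the endpoint and, after dropout, stays in ITT through last observation carried forward (SAP 5.3, 6.1). A control entering at 24 weeks decides whether to join when the Week 24 symptom state is already present and known to that subject, and has almost no time in which to drop out. If willingness to join depends on how the subject feels, the control result in that stratum is distorted. A later adjustment for RESTFUL baseline values would not remove selection on the outcome.

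The second issue is medication history. The Stable Medication population exists because the two arms have different instructions on changing medication. A late entrant's membership depends on one report covering the whole interval, so a forgotten change leaves an unstable control in that set. The table of RLS management changes over Weeks 1 to 24 (SAP 9.0) has the same weakness.

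**Working it through.** The plan gives no sample size, no count of Arm 2 entrants by time and no assumed responder rate, so there is no stated figure to reproduce.

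**1. Entry window.** Plus or minus 6 days is 6/7 = 0.86 week, so Section 16.12 admits 24-week entry from 23.1 to 24.9 weeks. Section 16.2, with plus or minus 1 week, admits it from 23 to 25 weeks. Table 3 is met only before 24.0 weeks. The Cohort 2B eligibility rule is not part of the conflict: its limit of under 24 weeks is counted back from the date on which "this protocol opens to enrollment are eligible for Arm 2", not from the subject's own consent.

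**2. Medication contacts up to Week 24.** These are counted from Protocol Table 4, Table 5 and the Arm 2 schedule. The gap is measured from RESTFUL completion or from the previous contact.

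| Group | ConMeds time points | Longest gap (weeks) | Weeks on study before Week 24 |
|---|---|---|---|
| Arm 1 | 8 | 4 | 24 |
| Arm 2, entry at 0 | 4 | 8 | 24 |
| Arm 2, entry at 8 | 3 | 8 | 16 |
| Arm 2, entry at 16 | 2 | 16 | 8 |
| Arm 2, entry at 24 | 1 | 24 | 0 |

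**3. Possible size of selection (all inputs assumed).** Let p be the true Week 24 responder rate among reachable former subjects, and c1 and c0 the consent probabilities of responders and non-responders. The observed rate among 24-week entrants is p·c1 / [p·c1 + (1 − p)·c0].

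| p | c1 | c0 | Observed rate | Shift (points) |
|---|---|---|---|---|
| 0.30 | 0.60 | 0.80 | 0.18/0.74 = 24.3% | −5.7 |
| 0.30 | 0.80 | 0.60 | 0.24/0.66 = 36.4% | +6.4 |
| 0.30 | 0.50 | 0.90 | 0.15/0.78 = 19.2% | −10.8 |
| 0.30 | 0.90 | 0.50 | 0.27/0.62 = 43.5% | +13.5 |
| 0.50 | 0.60 | 0.80 | 0.30/0.70 = 42.9% | −7.1 |
| 0.50 | 0.80 | 0.60 | 0.40/0.70 = 57.1% | +7.1 |
| 0.50 | 0.50 | 0.90 | 0.25/0.70 = 35.7% | −14.3 |
| 0.50 | 0.90 | 0.50 | 0.45/0.70 = 64.3% | +14.3 |

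The shift for the whole arm is the share f of 24-week entrants times the shift in the stratum. With f from 10% to 50%, it runs from 0.10 × 5.7 = 0.6 to 0.50 × 14.3 = 7.1 points, in either direction.

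**4. Effect on the test, if the shift is downward.** Take both true rates as 50%, 30 to 100 subjects per arm (assumed), and the one-sided 0.025 two-proportion test. A 2-point fall in the control rate raises the rejection rate to 0.036 (30 per arm) or 0.047 (100 per arm). A 5-point fall raises it to 0.058 or 0.105. An upward shift works against the device instead.

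**The case against.** **No score exists before consent.** A reader might infer that these controls are chosen after their outcome has been measured, or that the investigator knows it. The documents do not support that. Section 16.4 puts consent before every study-specific procedure except pre-screening. The criteria re-checked for Arm 2 (Section 7.1) include no symptom score, and no contact between RESTFUL exit and Arm 2 consent is described. What stands is self-selection by the subject, who sets the IRLS and PGI-I ratings (Section 16.14) and knows the recent symptoms.

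**The pull of Arm 3.** Section 4 says "A subject may be asked to participate in Arm 3 after completing Arm 2", and a reader might infer that symptomatic subjects join Arm 2 to reach the device. But Arm 2 is not stated as a condition for Arm 3. Arm 3 invitations under limited capacity follow the order of RESTFUL completion (Section 16.3.1), and the SAP describes only two arms. This does not settle the direction of bias.

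**Recall is not the only source.** RESTFUL concomitant-medication data are the recorded baseline (Section 16.7), so a net new drug or dose can be seen by comparing lists. Recall matters mainly for changes made and reversed within the interval, and for when a change occurred.

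**Few subjects may be affected.** RESTFUL enrolment began in May 2021 and treatment lasted 8 weeks, so the earliest completions fall around 26 June 2021. By the protocol date of 24 November 2021 that is 151 days, or 21.6 weeks. If completions were uniform over the 24-week Cohort 2B window and sites invited everyone at opening, about (24 − 16)/24 = one third of Cohort 2B would be past Week 16, and a smaller share of Arm 2 once Cohort 2A is added. Later opening or slower consent would raise this. Half of Arm 2 is therefore the high end of the illustration.

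**Evaluation 4 has a second definition.** The Arm 2 visit text in Section 16.12 counts it from Eval 1, which would separate consent from outcome. Section 16.2, Table 5 and the protocol's schedule footnote all count from RESTFUL completion, and the single SF-36 and medication assessment makes sense only on that reading.

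**The problem is graded.** Entrants at 8 and 16 weeks also know their symptoms at consent, and excluding late entrants raises the share of Cohort 2A, who declined Arm 1. This stands, and it is why the main analysis population should not be replaced.

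**Conclusion.** The inconsistency is plain on the text: Table 3 cannot be met by entry at or after 24.0 weeks, and the two tolerances differ. For controls who enter then, consent, outcome and exit coincide, with one medication contact over 24 weeks against eight in Arm 1.

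This weakens what #6-11 and the Stable Medication analysis can claim, by an amount the documents do not allow anyone to fix. The range of 0.6 to 7 points rests wholly on assumed responder rates, consent rates and shares, and its sign is open. It would be wrong to conclude that the bias favours the device. The primary endpoint and #1-5 do not use Arm 2 and are unaffected. The comparison is in any case open-label and non-randomised, so this adds one avoidable source of doubt to others.

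**What to change.** - **Protocol.** Make Table 3, Section 16.2, Section 16.12 and Table 5 state one Arm 2 entry window and one tolerance, and count Evaluation 4 from one date throughout.
- **Main analysis.** Keep all Arm 2 subjects in the ITT analysis of #6-11.
- **Reporting.** Flag each Arm 2 subject by recorded consent date, and report Arm 2 Week 24 results by entry time (0, 8, 16 and 24 weeks), with the number in each group.
- **Sensitivity analysis.** Pre-specify in the SAP a repeat of #6-11 and of the Stable Medication analysis that excludes 24-week entrants.
- **Interpretation.** State in advance that a positive result on #6-11 that does not hold in that analysis will be interpreted with caution.

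The cost is a wording change, one flag from dates already collected and a few more tables. The restricted analysis will have wider intervals and a higher share of Arm 1 decliners among its controls, so it should be read beside the full one and not in its place.

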16.14. Administration of assessments

- PGI-I (Patient Global Impressions Improvement Scale). The subject will determine the ratings, and the examiner should be available to clarify any misunderstandings the subject may have about the questions. The examiner or the subject may mark the subject's answers on the form.
- CGI-I (Clinical Global Impressions Improvement Scale). The CGI-I is completed by the Investigator after conducting a short interview with the subject regarding their RLS symptoms over the past week compared to baseline. The Investigator will not be permitted access to the subject's IRLS responses but will be permitted access to the subject's PGI-I responses.
- IRLS. The subject will determine the ratings, and the examiner should be available to clarify
 any misunderstandings the subject may have about the questions. The examiner or the subject
 may mark the subject's answers on the form.
- MOS-Sleep. The subject will determine the ratings, and the examiner should be available to clarify any misunderstandings the subject may have about the questions. The examiner or the subject may mark the subject's answers on the form.

Investigational Plan, Protocol CT-05 (Extension Study)

Document #: CT-4

Rev: 1.0

Effective: 11/24/2021

- SF-36. The subject will determine the ratings, and the examiner should be available to clarify any misunderstandings the subject may have about the questions. The examiner or the subject may mark the subject's answers on the form.
- o The Weekly Questionnaire will be completed by the subject.
- The Bi-weekly Questionnaire will be completed by the subject every 2 weeks during Weeks
 25-32 of Arms 1 and 3.
- Subject characterization will be completed by the examiner (site staff) based on information from the subject. Subject characterization information may be transferred from the database for the RESTFUL Study, if such information is available and has not changed.
- Medical history will be completed by the examiner (site staff) based on information from the subject. Medical history information may be transferred from the database for the RESTFUL Study, if such information is available and has not changed.

16.15. Study Exit

Study exit will occur at the conclusion of Eval #9. At study exit, the Investigator/coordinator will complete the study exit eCRF. Adverse events unresolved at study exit will be followed by the Investigator until resolution occurs or at least 30 days after the subject's participation in the study is complete.

16.16. Subject Discontinuation

A subject may be removed from the study prior to completion for any of the following reasons:

- Voluntary withdrawal of consent
- Adverse event preventing further study participation
- Investigator believes risk of further subject participation outweighs benefit
- Persistent non-compliance or lost to follow-up
- Pregnancy
- Subject no longer meets inclusion criteria
- [For arms 1 and 3 only] Subject makes a significant change to dosage of medications known to interfere with sleep or RLS symptoms, including sleep medications, antidepressants, sedative antihistamines.

Investigational Plan, Protocol CT-05 (Extension Study)

Document #: CT-4

Rev: 1.0

Effective: 11/24/2021

• [For arms 1 and 3 only] Insufficient device availability (see 16.16.1 below)

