7.1. Screening process differences for each Arm

Investigational Plan, Protocol CT-05 (Extension Study)

Document #: CT-4

Rev: 1.0

Effective: 11/24/2021

All subjects were screened for the eligibility criteria in Sections 7.2 and 7.3 upon entry to The RESTFUL Study, with the exception of IC #13 and EC #25-27. The following subset of eligibility criteria will be re-assessed at screening for CT-05, to confirm that they still apply:

- **Arm 1:** IC #8, 12-13. EC #7, 11*, 12, 14-17, 19, 21-27.
 - * except that acute infections with mild symptoms will not be exclusionary.
- Arm 2: IC #12-13. EC #12, 17, 21, 23, 25.
- **Arm 3:** IC #3-8, 10, 12-13. EC #2, 3, 6-12, 14-17, 19-27.

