7.2. Complete list of inclusion criteria (IC)

All subjects are required to meet the following inclusion criteria in order to be considered eligible for participation in this study:

- 1. Subject has received a medical diagnosis of primary restless legs syndrome (RLS).
- 2. Subject is refractory to RLS medication (as defined in section 7.3).
- 3. Subject has moderate-severe RLS symptoms as defined by a score of 15 or greater points on IRLS (International Restless Legs Syndrome Study Group Rating Scale [12]) over the week prior to study entry.
- 4. Subject has RLS symptoms 2 or more nights per week during the week prior to study entry as defined by a score of 2, 3, or 4 on IRLS question #7.
- 5. RLS symptoms are most significant in the subject's lower legs and/or feet.
- 6. RLS symptoms are most significant at bedtime, after bedtime, and/or in the 2 hours before bedtime.
- 7. RLS symptoms between 10am and 6pm are not severe.
- 8. Subject agrees to not change dosage or schedule of any medications that are known to impact RLS symptoms during the study, including RLS medications, antidepressants, sleep medications, or sedative antihistamines.
- 9. Subject agrees to not make major lifestyle changes during the study that would significantly affect bedtime, such as major changes to diet, exercise, or career.

Investigational Plan, Protocol CT-05 (Extension Study)

Document #: CT-4

Rev: 1.0

Effective: 11/24/2021

- 10. Subject possesses the necessary equipment, internet/phone accessibility, and communication ability to complete electronic questionnaires and respond to electronic communications and phone calls from the research staff throughout the in-home portion of the study.
- 11. Subject is \geq 22 and \leq 79 years of age when written informed consent is obtained.
- 12. Subject has signed a valid, IRB-approved informed consent form, can understand the requirements of the study and instructions for device usage, and can converse in English.
- 13. Subject previously completed the RESTFUL Study.

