16.1. Overview

Arms 1 and 3 involve a 24-week extension of in-home investigational device usage for subjects who previously completed the RESTFUL Study, followed by an 8-week period without investigational device usage to assess the progression of RLS following cessation of treatment. Two separate arms are employed to maximize the number of subjects eligible for any extension phase (Arm 1 and Arm 3) while also maximizing the number of subjects who can proceed directly to the extension phase (Arm 1 only). Notably, in the RESTFUL Study, subjects will have already completed either 4-weeks of device usage (Sham \rightarrow Active) or 8-weeks (Active \rightarrow Active) depending on randomization. Since site staff were blinded to RESTFUL Study treatment assignment, no procedures in this protocol will be affected by RESTFUL Study treatment assignment.

Arm 2 serves as a control arm with matched duration to the 24-week period of investigational device usage; this arm is designed to the assess the changes to medication and RLS symptoms that occur under the conventional standard of care, in the absence of investigational device intervention. Although the duration of Arm 2 states 24-weeks, each subjects participation will vary, since the 24-week period also includes the time between when the subject exits the RESTFUL study and when they enroll in Arm 2 of the CT-05 study. For example, subjects who are consented more than 8-wks after RESTFUL Study completion will only complete the remaining follow-ups (e.g. subjects consented 12-wks after the RESTFUL Study will only complete the 16-wk and 24-wk follow-ups).

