3.1 Overview

Subjects who previously completed the RESTFUL Study [Protocol Number: CT-04; ClinicalTrials.gov Identifier: NCT04874155] consent to one of two Arms, the design of which is

illustrated in the flowchart below (Figure 1). Arm 1 is a Direct Roll-Over Extension and Arm 2 is a Control.

- **Arm 1** (Direct Roll-Over Extension) Arm 1 is only an option for subjects who successfully complete RESTFUL Study after enrollment to CT-05 begins at a given clinical site; Arm 1 involves a 24-wk extension period of NTX100 device use followed by an 8-wk period without device use. Subjects in Arm 1 are instructed to maintain constant dose and schedule of RLS medication (if applicable).
- Arm 2 (Control Group) Arm 2 is an option for subjects who successfully complete the RESTFUL Study before enrollment to CT-05 begins at a given clinical site or subjects who decline to participate in Arm 1. Subjects enrolled in Arm 2 will receive no treatment with the NTX100 device during Arm 2. Arm 2 involves assessment during the 24-wks after RESTFUL Study completion. Subjects in Arm 2 are permitted to change RLS medication.

Figure 1: Study Design Flowchart

The schedule of assessments for this study is presented in Table 1.

Table 1: Schedule of Assessments

	Eval 1			Eval 2	Eval 3	Eval 4	Eval 5	Eval 6	Eval 7	Eval 8	Eval 9	
	Day 0	Wks 1-24	Wks 25-32	Wk-2	Wk-4	Wk-8	Wk-12	Wk-16	Wk-20	Wk-24	Wk-32	
	In-person	Remote	Remote	Remote	Remote	In-person or Remote**			Remote	In-person	Remote	
Completed by												
	X											
	X											
Staff + subject	X											
Subject		X										
Subject			х									
Staff				X	X	x	X	x	X	X		
Staff	X			Х	Х	x	X	Х	Х	х	X	
Staff				X	Х	x	X	x	X	Х	X	
Staff + subject				Х	Х	x	Х	Х	Х	х	X	
Staff + subject				X	X	x	X	x	X	X	X	
Investigator + subject						х		х		Х	X	
Staff + subject					Х	x	X	Х	х	х	X	
Staff + subject	X									х		
Staff + subject										х		
Staff + subject											X	
Staff + subject	X **					X **		X **				
	* Data from Eval	11 of the RE	STFUL Study	will be us	ed, since b	oth Evals typic	cally occu	r on the same	day			
	Staff + subject Subject Subject Staff Staff Staff Staff Staff + subject Staff + subject Investigator + subject Staff + subject	In-person	Day 0 Wks 1-24 In-person	Day 0	Day 0 Wks 1-24 Wks 25-32 Wk-2	Day 0	Day 0	Day 0	Day 0	Day 0 Wks 1-24 Wks 25-32 Wk-2 Wk-4 Wk-8 Wk-12 Wk-16 Wk-20 In-person or In-pe	Day 0 Wks 1-24 Wks 25-32 Wk-2 Wk-4 Wks-4 Wks-12 Wk-16 Wk-20 Wk-24	Day 0

		Eval 1	Eval 2	Eval 3	Eval 4	

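### Protocol 16.16 allows removal in any arm for no longer meeting unnamed inclusion criteria, which conflicts with what Arm 2 is meant to observe and can put carried-forward values in place of Week 24 data

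*Protocol*

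**What the plan says.** Protocol 16.16 opens permissively: "A subject may be removed from the study prior to completion for any of the following reasons". One listed reason is "Subject no longer meets inclusion criteria". It carries no arm tag and no list of criteria. The next reason does carry a tag: "For arms 1 and 3 only] Subject makes a significant change to dosage of medications known to interfere with sleep or RLS symptoms".

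The inclusion criteria in Protocol 7.2 apply to all subjects. IC #7 reads "RLS symptoms between 10am and 6pm are not severe". IC #8 begins "Subject agrees to not change dosage or schedule of any medications that are known to impact RLS symptoms during the study". Protocol 7.1 lists the criteria to be re-assessed at CT-05 screening. For Arm 2 the list is "IC #12-13. EC #12, 17, 21, 23, 25", so neither IC #7 nor IC #8 is among them.

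Protocol 16.1 says Arm 2 is there to assess "changes to medication and RLS symptoms that occur under the conventional standard of care". Protocol 16.10 exempts Arm 2 from the stable-medication instruction, and Protocol 17.2.4 lists change in RLS medication as an outcome compared between Arms 1 and 2. SAP 3.1 states: "Subjects in Arm 2 are permitted to change RLS medication".

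On handling, SAP 6.1 makes the ITT set (all eligible enrolled subjects) primary for efficacy. SAP 5.3 and 8.1 fill missing efficacy values by LOCF, going back to CT-04 if the subject has no CT-05 value. The Per Protocol definition in SAP 6.3 excludes anyone who discontinues.

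**The concern.** An entry criterion describes who may start. When it also serves as a ground for removal, any criterion that the disease course or its treatment can overturn makes removal depend on outcome. Here the bullet can reach symptom progression in every arm and, in Arm 2, the medication changes that arm was set up to record.

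The Week 24 value of a removed subject is not observed. The study is open-label at seven sites (SAP 3.3, 5.5), and each site would have to decide for itself what the bullet covers. At stake are the Arm 1 Week 24 CGI-I rate, the Arm 1 versus Arm 2 comparisons (key secondary endpoints 6 to 11), and the tabulation of changes in RLS management in SAP 9.0. SAP 5.3 imputes efficacy endpoints only, so medication changes after removal are not recovered.

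**Working it through.** The documents give no figure on this point. SAP 3.4 reports that no sample size was determined, and no removal rate is stated. The check is therefore mainly textual, followed by an illustration on assumed values.

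**Step 1. Which inclusion criteria can be lost during the study, on their own wording (Protocol 7.1, 7.2)?**

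| Criterion | Time anchor | Re-assessed at CT-05 screening | Can be lost later? |
|---|---|---|---|
| IC #3 (IRLS total), #4 (IRLS question 7) | Week before study entry | Arm 3 only | No |
| IC #5, #6, #7 (site, timing, daytime severity) | None | Arm 3 only | Yes, if symptoms shift or progress |
| IC #8 (no change of relevant medication) | Whole study | Arms 1 and 3 | Yes, if medication changes |

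**Step 2. Does another passage settle the scope?** Section 7.1 governs screening only, and 16.16 does not refer to it. Section 16.10, SAP 3.1 and the next bullet of 16.16 all leave Arm 2 free to change medication. The untagged bullet, read with IC #8, reopens for Arm 2 a ground that its neighbour confines to Arms 1 and 3. No passage says which prevails.

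**Step 3. What value replaces Week 24 after removal?**
- Arm 1 CGI-I is scheduled at Weeks 8, 16, 24 and 32 (Protocol Table 4). After removal between Week 8 and Week 24, the Week 8 or Week 16 rating is used. After removal before Week 8, the CT-04 rating is used.
- Arm 2 scales are scheduled at Weeks 8, 16 and 24 only. A subject enrolled at 0 weeks and removed before Week 8 has no CT-05 value and takes the CT-04 one. Both RESTFUL sequences end on active device (Protocol 16.1), so an on-device score would represent no-device control.
- Section 16.16.1 requires an exit form. Neither document provides for efficacy assessment after removal.

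**Step 4. Illustration for the Arm 1 CGI-I rate.** Assume 50 subjects, of whom 30 are true Week 24 responders (30/50 = 60%), and *k* worsened non-responders who are removed.
- ITT with LOCF, last CGI-I already a non-response: 30/50 = 60%, no change.
- ITT with LOCF, last CGI-I still a response: (30 + *k*)/50. For *k* = 2, 4, 6 this is 32/50 = 64%, 34/50 = 68%, 36/50 = 72%.
- Per Protocol or observed cases, with no other exclusions: 30/(50 − *k*) = 30/48 = 62.5%, 30/46 = 65.2%, 30/44 = 68.2%.

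**Step 5. Illustration for mean IRLS under LOCF.** Shift in an arm mean = share removed × gap between the carried-forward and the unobserved Week 24 score. Assuming 5% to 20% removed and a gap of 3 to 8 points, the shift runs from 0.05 × 3 = 0.15 to 0.20 × 8 = 1.6 points.

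**Step 6. Direction for Arm 1 versus Arm 2.** A removed Arm 1 worsener keeps a better earlier score, which favours NTX100. A removed Arm 2 worsener also keeps a better score, which works against NTX100. An Arm 2 subject removed at a medication change that helps keeps a worse score, which favours NTX100. The net sign is not determined.

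**The case against.** The strongest reply is that the specific passages point one way. Section 7.1 asks Arm 2 to meet only IC #12-13 among the inclusion criteria. Section 16.10, SAP 3.1 and SAP 3.2 exempt Arm 2 from medication stability, and the adjacent bullet limits medication-change removal to Arms 1 and 3. Against these stands one generic, discretionary line, and the schedules place screening only at Eval 1, with no later eligibility check. In Arm 1, IC #5-7 are not re-assessed at entry to CT-05, so it would be odd for them to become removal grounds afterwards. Medication change in Arms 1 and 3 is already a separate ground, so the bullet adds little there. Finally, the ITT set keeps removed subjects.

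Much of this stands. It shows that the sponsor probably did not intend to remove Arm 2 medication changers, and that nothing prompts removal on a schedule. It does not settle the text, because 7.1 is confined to screening and 16.16 names neither criteria nor arms. Keeping subjects in the ITT set by LOCF does not recover the Week 24 state, as Step 3 shows.

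A reader might go further and infer that a subject could be removed because the device worked, having fallen below the IRLS or symptom-frequency threshold. The documents do not support that: IC #3 and #4 are tied to the week before study entry, and Arm 1 does not re-assess them.

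**Conclusion.** The point holds as an unresolved conflict in the protocol that should be corrected. It is not an instruction to remove subjects for outcome events. The bullet is open to any arm, and IC #5-8 can be lost through events the study follows. The affected Week 24 values would then come from LOCF in the ITT set and be absent from the Per Protocol set.

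Size and net direction are unknown. The 64% to 72% range assumes 50 subjects, 30 true responders, and removed worseners whose last CGI-I was still a response. If that last rating was already a non-response, the ITT rate does not move. The 62.5% to 68.2% range applies only to an observed-case or Per Protocol analysis and should not be read as an effect on the primary result.

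**What to change.** Reconcile Protocol 7.1, 7.2, 16.1, 16.10 and 16.16 with SAP 3.1, so that 16.16 states which inclusion criteria the bullet covers in each arm. Which clinical grounds for removal are kept is for the sponsor to decide.

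For subjects removed on this ground, collect CGI-I, PGI-I, IRLS and MOS-Sleep remotely at the scheduled Week 24 date unless consent is withdrawn, and use those values in the ITT analysis in place of LOCF. Arm 2 Week 24 is already remote. Protocol 18 sets out remote visits for Arm 1 but does not provide for follow-up after removal, so a sentence is needed there or in 16.16, with a matching line in SAP 5.3.

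The cost is one reworded bullet, one added sentence, the SAP line and a few extra calls. Some less favourable values will enter the result, and in Arm 1 they may be recorded off device.
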